## 5. BASELINE CHARACTERISTICS

### 5.1. Demographics and Baseline Characteristics

Participant demographic data (eg, sex, race/ethnicity, age, and age group (<18,  $\geq 18$  - < 60,  $\geq 60$ ) and baseline characteristics (eg, body weight, height, and body mass index [BMI]) will be summarized by treatment group and overall using descriptive statistics (n, mean, SD, median, Q1, Q3, minimum, and maximum) for continuous data and by the number and percentage of participants for categorical data. The summaries of demographic data and baseline participant characteristics will be provided for the Safety Analysis Set.

For categorical data, the Cochran-Mantel-Haenszel (CMH) test (ie, general association statistic for nominal data and row mean scores for ordinal data) will be used to compare the 2 treatment groups. For continuous data, the 2-sided Wilcoxon rank sum test will be used to compare the 2 treatment groups.

Similar summaries will be produced for the following subgroups: region (US vs. ex-US), participant's age (< 60 vs  $\geq 60$  years), and participants who reside in a skilled nursing facility (Yes, No).

A by-subject demographic listing will be provided.

### 5.2. Other Baseline Characteristics

The following baseline disease characteristics will be summarized by treatment group and overall using descriptive statistics:

- Baseline risk factor as defined in Section 3.4
- Duration of symptoms prior to first dose of study drug
- Duration from SARS-CoV-2 nucleic acid/antigen confirmation to first dose of study drug
- Alanine aminotransferase (ALT)
- Aspartate aminotransferase (AST)
- Baseline SARS-CoV-2 viral Load (as a continuous variable, and a categorical variable with categories of < median and  $\geq$  median)
- Baseline respiration rate

For categorical data, the CMH test (general association statistic for nominal data) will be used to compare the 2 treatment groups. For continuous data, the 2-sided Wilcoxon rank sum test will be used to compare the 2 treatment groups. Similar summaries will be produced for the following

subgroups: region (US vs. ex-US), participant's age (< 60 vs  $\geq$ 60 years), and participants who reside in a skilled nursing facility (Yes, No).

Categorical baseline COVID-19 symptoms from Flu-PRO Plus will be summarized by treatment group separately from other baseline characteristics.

### **5.3. Medical History**

Any medical condition or clinically significant laboratory abnormality with an onset date before the consent form is signed and not related to a protocol-associated procedure is considered to be preexisting and should be documented as medical history. General medical history data will be collected at screening. It will be coded using the current version of MedDRA. A summary table will present the percentages of participants reporting each medical history preferred term, sorted first in alphabetical order by system organ class (SOC) and then by preferred term (PT) in descending order of total frequency within SOC.

## 6. EFFICACY ANALYSES

### 6.1. Primary Efficacy Endpoint

#### 6.1.1. Definition of the Primary Efficacy Endpoint

The primary endpoint of the study is the composite endpoint of COVID-19 related hospitalization (defined as at least 24 hours of acute care) or all-cause death by Day 28. The endpoint will be derived by combining the available all-cause death and COVID-19 related hospitalization reported by the site. The first COVID-19 related hospitalization will be used for the proportion of COVID-19 related hospitalization or all-cause death.

#### 6.1.2. Statistical Hypothesis for the Primary Efficacy Endpoint

**Null hypothesis:** The hazard ratio of COVID-19 related hospitalization or all-cause death by Day 28 between the 2 treatment groups equals to 1.

**Alternative hypothesis:** The hazard ratio of COVID-19 related hospitalization or all-cause death by Day 28 between the 2 treatment groups does not equal to 1.

#### 6.1.3. Primary Analysis of the Primary Efficacy Endpoint

The hazard ratio of COVID-19 related hospitalization or all-cause death between the two treatment groups will be estimated using a Cox model with stratification factors as covariates.

If a participant prematurely discontinues from the study prior to Day 28 or the hospitalization status is missing, the participant is censored at last study date or day 28 whichever is earlier. If a participant has a COVID-19 related hospitalization first and then dies, then date of the COVID-19 related hospitalization and status will be used for the primary analysis for this participant. If a participant has a non COVID-19 related hospitalization first and then dies without experiencing a COVID-19 related hospitalization, then date of the death and status will be used for the primary analysis for this participant.

The hazard ratio, p-value, 95% CI for the hazard ratio from Cox model, and proportion of COVID-19 related hospitalization or all-cause death at Day 28 from Kaplan-Meier estimate will be provided.

The FAS will be the primary analysis set for efficacy endpoint evaluation. The primary endpoint may be analyzed for each of the subgroups defined in Section 3.3.

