### **8.9. Sample Size**

The total sample size of the study will be approximately 1264 participants.

The sample size computation is based on proportions of COVID-19 related hospitalization or all-cause death by Day 28 for the RDV and placebo treatment groups. The sample size needed for a 1:1 randomization using a 2-tailed test at level  $\alpha$  is given by:

$$\frac{(z_{1-\alpha/2} + z_{1-\beta})^2}{P(1 - R^2)\sigma^2 B^2}$$

Where P is the overall rate of COVID-19 related hospitalization or all-cause death, B is the log hazard ratio,  $\sigma$  is the standard deviation of treatment indicator variable, R is the R-Squared that is obtained when treatment indicator variable is regressed on the other covariates, and  $z_{1-\alpha/2}$  and  $z_{1-\beta}$  are the 1- $\alpha/2$  and 1- $\beta$  quantiles of the standard normal distribution.

A sample size of 1264 participants (632 in each group with 1:1 randomization) achieves > 90% power to detect a ratio of 0.55 (RDV to placebo in proportion of COVID-19 related hospitalization or all-cause death, which is equal to a hazard ratio of 0.534) using a 2-sided significance level of 0.05 assuming the overall hospitalization or death rate is 9.3% (12% in the placebo group and 6.6% in the RDV group) and a 5% drop out rate. The sample size provides approximately 80% power to detect smaller treatment effect size with a ratio of 0.60 (RDV to placebo), assuming a 2-sided significance level of 0.05 and the overall hospitalization or death rate is 9.6% (12% in the placebo group and 7.2% in the RDV group) and a 5% drop out rate.

The sample size calculation was done using software PASS (Version 14.0, module of Cox regression for survival).

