### **3.6. Missing Data and Outliers**

#### **3.6.1. Missing Data**

In general, missing data will not be imputed unless methods for handling missing data are specified. Exceptions are presented in this document.

Participants with missing outcomes for the primary endpoint due to premature discontinuation of the study will be censored at last study date.

In this study, a missing pre-treatment laboratory result would be treated as normal (ie, no toxicity grade) for the laboratory abnormality summary. The handling of missing or incomplete dates for AE onset is described in Section 7.1.6.2, and for prior and concomitant medications in Section 7.4.

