### 3.8. Analysis Visit Windows

#### 3.8.1. Definition of Study Day

Study day will be calculated from the first dosing date of study drug and derived as follows:

- For postdose study days: Assessment Date – First Dosing Date + 1
- For days prior to the first dose: Assessment Date – First Dosing Date

Therefore, study day 1 is the day of first dose of study drug administration.

**Last Dose Date** is defined as the maximum, nonmissing, nonzero dose end date of treatment recorded on the Study Drug Administration eCRF form with “Study Drug Permanently Withdrawn” box checked for participants who prematurely discontinued or completed study drug according to the Study Drug Completion eCRF. Refer to [Appendix 2](#) for missing date imputation, if necessary.

**Last Study Date** is the latest of the study drug start dates and end dates, the in-person or phone visit dates, the vital sign or respiratory status collection dates, Flu-PRO Plus questionnaire collection date and the laboratory collection dates, including the 28-day follow-up visit date, and the death date (if applicable, only for participants who prematurely discontinued study according to the Study Completion eCRF).

**Baseline value** is defined as the last value obtained on or prior to the first dose date (and time, if available) unless otherwise specified (see Section [3.8.3](#)).

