#### 6.1.4. Secondary Analyses of the Primary Efficacy Endpoint

Sensitivity analyses maybe conducted using the following alternative approaches for the primary endpoint.

- A CMH test including baseline stratification factors as strata for the statistical comparison between the two treatment groups. If a participant prematurely discontinues from the study prior to Day 28 with no event before discontinuation or the hospitalization/death status is missing, the participant will be considered as with no hospitalization/death.

The analysis is for the purposes of evaluating the robustness of the estimates of the primary analysis.

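### The primary censoring rule in SAP 6.1.3 and Appendix 2 item 13 omits the condition that no event has yet occurred, and so conflicts with SAP 3.6.1, 6.1.1 and 6.1.4 and with Protocol 8.5.1

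*SAP*

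**What the plan says.** The primary analysis is a Cox model for time to COVID-19 related hospitalization or all-cause death by Day 28. SAP 6.1.3 sets its censoring rule: "If a participant prematurely discontinues from the study prior to Day 28 or the hospitalization status is missing, the participant is censored". The censoring time is the earlier of Day 28 and the last study date. Appendix 2 item 13 of the SAP, in the programming specifications, repeats the rule.

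Two further sentences in 6.1.3 deal with sequences. A COVID-19 hospitalization followed by death counts at the hospitalization date. A non-COVID-19 hospitalization followed by death, with no COVID-19 hospitalization, counts at the death date. Item 13 repeats neither.

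Other places put the rule differently:

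- SAP 3.6.1: "Participants with missing outcomes for the primary endpoint due to premature discontinuation of the study will be censored at last study date". Protocol 8.5.1 likewise censors only missing outcomes, at last contact.
- SAP 6.1.1 derives the endpoint from the deaths and COVID-19 hospitalizations that are available, using the first such hospitalization.
- SAP 6.1.4, for the CMH sensitivity analysis, counts as a non-event a participant who meets this condition: "If a participant prematurely discontinues from the study prior to Day 28 with no event before discontinuation or the hospitalization/death status is missing".

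SAP 3.8.1 includes the death date in Last Study Date, "only for participants who prematurely discontinued study according to the Study Completion eCRF". SAP 6.2.1 applies the 6.1.3 method to the Day 14 composite and to both MAV composites.

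**The concern.** The trigger in 6.1.3 and item 13 is a status (early discontinuation, or missing hospitalization status), not the absence of an event. Three kinds of participant are exposed if the sentence is coded as it stands:

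1. Hospitalized for COVID-19, then withdraws alive before Day 28. Neither sequence sentence covers this. Protocol 6.6 allows withdrawal where continued follow-up is not possible or acceptable.
2. Dies without a prior hospitalization and is recorded as a premature discontinuation. The definition of Last Study Date suggests that such records can exist.
3. Dies with hospitalization status missing. The primary rule looks at hospitalization status alone, whereas 6.1.4 looks at hospitalization and death status.

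The first case follows directly from the text. The second and third are possible, but depend on how deaths are recorded.

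SAP 3.5 rests the efficacy conclusion on this endpoint alone, at the 0.05 level. An observed event turned into a censored time would be lost from both the Cox model and the Kaplan-Meier proportions, while the CMH sensitivity analysis would still count it. The two analyses would then differ in their events as well as their method.

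**Working it through.** **Inputs.** Protocol 8.9: "using a 2-sided significance level of 0.05"; "achieves > 90% power to detect a ratio of 0.55"; "which is equal to a hazard ratio of 0.534"; "12% in the placebo group and 6.6% in the RDV group"; 1264 participants allocated 1:1; 5% dropout. SAP 2.1.1: 584 randomized when enrollment stopped. The documents do not give the share *q* of participants with an event who later leave before Day 28; it is an assumption here.

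**The plan's own figure.**

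- HR = ln(1 − 0.066) / ln(1 − 0.12) = 0.534, as stated.
- Expected events D = 1264 × 0.95 × 0.093 = 111.7.
- Power = Φ(|ln HR| × √(D/4) − 1.96) = Φ(0.627 × 5.284 − 1.96) = 0.912. This is the plan's Cox formula with R² = 0, and it agrees with the stated power above 90%.

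**At 584 randomized, with no event lost.**

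- Placebo: 292 × 0.95 × 0.12 = 33.3 events.
- RDV: 292 × 0.95 × 0.066 = 18.3 events.
- Total 51.6; power = Φ(0.627 × √(51.6/4) − 1.96) = 0.615.

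The fall from 91% to 61.5% comes from stopping enrollment, not from the censoring rule.

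**Literal rule, equal loss in both arms.** Events become 51.6 × (1 − q), with HR held at 0.534 for power:

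| q (assumed) | Events lost | Events left | Power |
|---|---|---|---|
| 0 | 0 | 51.6 | 61.5% |
| 5% | 2.6 | 49.0 | 59.3% |
| 10% | 5.2 | 46.4 | 57.0% |
| 20% | 10.3 | 41.3 | 52.2% |

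The HR hardly moves. At q = 5% it is ln(1 − 0.066 × 0.95) / ln(1 − 0.12 × 0.95) = 0.535; at 10% it is 0.536.

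**Literal rule, unequal loss** (illustrative; approximate HR from the reduced proportions):

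- 10% of placebo events only: ln(1 − 0.066) / ln(1 − 0.108) = 0.597.
- 10% of RDV events only: ln(1 − 0.0594) / ln(1 − 0.12) = 0.479.

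The bias can therefore go either way, depending on which arm loses events.

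**The case against.** The best defence is that the SAP, read as a whole, already gives the right rule. A participant with an observed hospitalization has no missing outcome, so SAP 3.6.1 and Protocol 8.5.1 do not censor that participant, and 6.1.1 uses the events that are available. Item 13 is terse throughout. Its entries for viral negativity and symptom alleviation also say only when participants are censored, yet nobody would read them as censoring everyone; for alleviation, SAP 6.2 supplies the missing condition. The protocol also works against the exposed case: follow-up is to continue after dosing stops (6.6), and the Day 28 contact may be by phone (6.5).

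Much of this stands. It settles the intent, and it rules out several stronger conclusions that a reader might draw:

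- *That the SAP makes no exception for observed events.* Section 6.1.3 keeps them in two sequences ending in death; only item 13, read alone, has no exception.
- *That deaths would be removed from the composite.* The Last Study Date definition only suggests that a death may be recorded as a discontinuation. It does not say that all deaths are, or that any is censored.
- *That the hazard ratio would be pulled toward 1.* This needs more placebo than RDV participants to leave after an event, and the documents give no basis for assuming so.

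What the defence does not remove is that the most specific statement of the primary rule, the one a programmer would code from, disagrees with the general ones. The authors wrote the condition explicitly for the sensitivity analysis in 6.1.4 and left it out for the primary analysis.

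**Conclusion.** The point holds as an internal inconsistency in the rule for the only confirmatory analysis. Followed exactly, 6.1.3 and item 13 would censor a COVID-19 hospitalization in a participant who later leaves alive before Day 28. They might also censor a death without prior hospitalization, depending on how discontinuation and hospitalization status are recorded. The intended rule is clear from SAP 3.6.1, 6.1.1 and 6.1.4 and from Protocol 8.5.1, so the documents do not support reading this as a decision to discard events.

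Its size cannot be fixed from the documents. The range shown rests on planning event rates, 5% dropout and an assumed share leaving after an event. Equal loss of 5% to 20% costs roughly 2 to 9 percentage points of power and leaves the hazard ratio almost unchanged. Unequal loss biases it in a direction that cannot be presumed. If no participant leaves after an event, there is no effect. The wording should be corrected, because with about 52 expected events even a few misclassified ones matter and the correction is simple.

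**What to change.** In SAP 6.1.3 and Appendix 2 item 13:

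1. Censor only participants with no COVID-19 related hospitalization or death on or before discontinuation, at the earlier of last study date and Day 28.
2. Count any COVID-19 related hospitalization or death known to have occurred by Day 28 as an event at the date of the first such event, whatever the later discontinuation.
3. Base the missing-status condition on hospitalization and death together, as 6.1.4 does, so that a known death is not censored because hospitalization status is missing.

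The change carries through 6.2.1 to the Day 14 and MAV composites; for the MAV composites the qualifying event is a COVID-19 related MAV or death, and the time limit is that of the endpoint.

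The cost is a short edit in two places before database finalization. No new data are needed. If the programs already exist, list the participants who have both an event and a premature discontinuation and confirm how each is coded.

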#### 6.1.4. Secondary Analyses of the Primary Efficacy Endpoint

Sensitivity analyses maybe conducted using the following alternative approaches for the primary endpoint.

- A CMH test including baseline stratification factors as strata for the statistical comparison between the two treatment groups. If a participant prematurely discontinues from the study prior to Day 28 with no event before discontinuation or the hospitalization/death status is missing, the participant will be considered as with no hospitalization/death.

The analysis is for the purposes of evaluating the robustness of the estimates of the primary analysis.

## 6.2. Secondary Endpoints

The other endpoints of interest include:

- Composite endpoint of COVID-19 related MAVs (medical visits attended in person by the participant and a health care professional) or all cause death by Day 28
- All-cause mortality by Day 28
- Proportion of participants hospitalized (COVID-19 related) by Day 28
- Composite endpoint of COVID-19 related hospitalization (defined as at least 24 hours of acute care) or all-cause death by Day 14
- Composite endpoint of COVID-19 related MAVs (medical visits attended in person by the participant and a health care professional) or death by Day 14
- Time-weighted average change in SARS-CoV-2 viral load from baseline to Day 7
  - The time-weighted average change from baseline to study Day 7 (DAVG7) in SARS-CoV-2 viral load (log10 copies/mL) is defined as the time-weighted average between the first postbaseline value through the last available value up to Day 7 minus the baseline value in SARS-CoV-2 viral load (log10 copies/mL). DAVG7 is calculated using the trapezoidal rule and the area-under-the-curve (AUC) concept as follows:

$$DAVG_7 = \frac{AUC_{t_1-t_7}}{(t_7 - t_1)} - Y_0$$

The AUC between  $t_1$  and  $t_n$  in a time (ie, day) versus SARS-CoV-2 viral load (log10 copies/mL) plot is calculated as

$$AUC_{t_1-t_n} = \sum_{i=1 \text{ to } (n-1)} \frac{1}{2} (Y_i + Y_{i+1}) \times (t_{i+1} - t_i)$$

Where  $Y_i$  is the SARS-CoV-2 viral load (log10 copies/mL) at time  $t_i$ ,  $t_1$  is the first postbaseline time, and  $Y_0$  is the baseline SARS-CoV-2 viral load (log10 copies/mL).

- For subject with SARS-CoV-2 viral load data only available up to Day  $x$  ( $x < 7$ ),  
$$DAVG_7$$
 is defined as  $DAVG_7 = \frac{AUC_{t_1-t_x}}{(t_x - t_1)} - Y_0$
- If baseline viral load is missing or there is no post-baseline data, then the participant will be excluded from the analysis. If there is one post-baseline data value  $Y_i$ ,  $DAVG_7 = Y_i - Y_0$ . If a participant receives additional COVID-19 treatments (see [Appendix 2](#)), the viral load from the start of additional treatment will be excluded.
- Time to alleviation (mild or absent) of baseline COVID-19 symptoms as reported on the COVID-19-adapted FLU-PRO Plus
  - The alleviation of baseline COVID-19 symptoms, i.e. overall alleviation of all symptoms scored 1 or higher at baseline for each participant, is defined as:
    - Symptoms scored as 2 or higher at baseline are scored as 0 or 1 at postbaseline, AND
    - Symptoms scored as 1 at baseline are scored as 0 at postbaseline, AND
    - for two consecutive days.
  - Time to alleviation of baseline COVID-19 symptoms is defined (in days) as:

First Date of the two consecutive dates achieving alleviation - First dose Date + 1

If a participant has not achieved symptom alleviation at last FLU-PRO Plus assessment or early discontinuation of study, the participant will be censored at last FLU-PRO Plus assessment date. Last assessment date is the last date when at least one of the baseline symptoms is assessed.
- Worsening after alleviation of baseline COVID-19 symptoms
  - The worsening after alleviation of baseline COVID-19 symptoms is defined as:
    - For a participant who has achieved alleviation of baseline COVID-19 symptoms
    - If any symptom scored as 2 or higher at baseline is scored as 2 or higher postbaseline after achieved alleviation, or
    - Any symptom scored as 1 at baseline are scored as 1 or higher postbaseline after achieved alleviation.
- Proportion of participants progressing to requiring oxygen supplementation by Day 28

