### 3. STUDY DESIGN

#### 3.1. Endpoints

The primary endpoints of this study are as follows:

- Composite endpoint of COVID-19 related hospitalization (defined as at least 24 hours of acute care) or all-cause death by Day 28
- Proportion of participants with treatment-emergent AEs

The secondary endpoints of this study are as follows:

- Composite endpoint of COVID-19 related MAVs (medical visits attended in person by the participant and a health care professional) or all-cause death by Day 28
- All-cause mortality at Day 28
- Proportion of participants hospitalized by Day 28
- Composite endpoint of COVID-19 related hospitalization (defined as at least 24 hours of acute care) or all-cause death by Day 14
- Composite endpoint of COVID-19 related MAVs (medical visits attended in person by the participant and a health care professional) or all-cause death by Day 14
- Time-weighted average change in SARS-CoV-2 viral load from baseline to Day 7
- Time to alleviation (mild or absent) of baseline COVID-19 symptoms as reported on the COVID-19-adapted FLU-PRO Plus
- Proportion of participants progressing to requiring oxygen supplementation by Day 28

CCI

[REDACTED]

[REDACTED]

[REDACTED]

[REDACTED]

[REDACTED]

[REDACTED]

[REDACTED]

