## **8.5.2. Secondary Analyses**

The secondary endpoint of COVID-19 related hospitalization or all-cause death by Day 14, COVID-19 related MAVs (medical visits attended in person by the participant and a health care professional) or death by Day 28, and COVID-19 related MAVs (medical visits attended in person by the participant and a health care professional) or death by Day 14 will be analyzed similarly as in the primary analysis. The all-cause mortality at Day 28 will be compared between the 2 treatment groups using a Fisher exact test. The proportion of participants hospitalized by Day 28 and the proportion of participants progressing to requiring oxygen supplementation by Day 28 will be estimated using the Kaplan-Meier method and compared between the 2 treatment groups using a log-rank test. Other endpoints of interest related to proportion of participants will be compared between treatment groups using a chi-square test or Fisher exact test. Endpoints that are measured as time to first event will be compared between treatment groups using the log-rank test and continuous endpoints will be compared between treatment groups using a Wilcoxon rank sum test or analysis of variance model.

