### **2.3. Changes from Protocol-Specified Analyses**

The DMC analysis was not performed due to the stop of enrollment on 08 April 2021 after less than 50% of the participants were randomized. The reasons of stopping enrollment were due to significant changes in the epidemiology of COVID-19 from a combination of lower hospitalization rates and high vaccine rates in high-risk patients, and a change in the unmet patient need for convenient at home options for non-hospitalized patients with COIVD-19. The decision to stop study enrollment was documented on 06-APR-2021 Study Management Team meeting minutes.

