### 6.2.1. Analysis of Secondary Endpoints

The FAS will be the primary analysis set for secondary endpoints. The mFAS will be used for secondary endpoints of composite endpoint of COVID-19 related MAVs or death.

All-cause mortality by Day 28 will be compared between the 2 treatment groups using the Fisher exact test. If a participant prematurely discontinues from the study prior to Day 28 or the Death status is missing, the participant will not be included in the analysis.

The secondary endpoint of COVID-19 related hospitalization or all-cause death by Day 14, COVID-19 related MAVs or death by Day 28, and COVID-19 related MAVs or death by Day 14 will be analyzed using the same method as used for the primary endpoint, described in Section 6.1.3.

The proportion of participants hospitalized (COVID-19 related) by Day 28 will be estimated using the Kaplan-Meier method and compared between the 2 treatment groups using a log-rank test. Hazard ratio and two-sided 95% CI estimated using the Cox regression with baseline stratification factors as covariates will be provided.

Number and percentage of participants progressing to requiring oxygen supplementation by Day 28 will be summarized and compared between treatment groups using the Fisher Exact test. Participants discontinued from the study before progressing to requiring oxygen supplementation will be considered as not requiring oxygen supplementation.

The Kaplan-Meier product limit method will be used to estimate and log-rank test will be used to compare treatment groups for the time to alleviation of baseline COVID-19 symptoms. Hazard ratio and two-sided 95% CI estimated using the Cox regression with baseline stratification factors as covariates will be provided. Number and proportion of participants with worsening after alleviation of baseline COVID-19 symptoms will be summarized.

Time-weighted average change in SARS-CoV-2 viral load from baseline to Day 7 will be summarized by treatment groups and compared between treatment groups using an ANCOVA model with baseline viral load as covariate, the analysis will be based on the Virology Analysis Set.

CC1

[REDACTED]

[REDACTED]

[REDACTED]

[REDACTED]

[REDACTED]

[REDACTED]

[REDACTED]

[figure not shown]
[REDACTED]

[REDACTED]

CCI

CCI

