#### **6.4. Change from Protocol Specified Efficacy Analyses**

The protocol states that the proportion of participants progressing to requiring oxygen supplementation by Day 28 will be estimated using the Kaplan-Meier method and compared between the 2 treatment groups using a log-rank test. In the SAP, the number and percentage of participants progressing to requiring oxygen supplementation by Day 28 will be summarized and compared between treatment groups using the Fisher Exact test due to very small number of participants progressing to requiring oxygen supplementation.

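### The SAP narrows the protocol's secondary endpoint of hospitalization by Day 28 to COVID-19 related admissions and does not list this as a change from the protocol

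*SAP*

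**What the plan says.** The protocol names the endpoint "Proportion of participants hospitalized by Day 28" in Section 3.1, with the same wording in the synopsis and in Section 8.1.3. The analysis text in Section 8.5.2 again has no cause qualifier: "The proportion of participants hospitalized by Day 28 and the proportion of participants progressing to requiring oxygen supplementation by Day 28" are to be estimated by Kaplan-Meier and compared by log-rank test.

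SAP 6.2 lists it as "Proportion of participants hospitalized (COVID-19 related) by Day 28". SAP 6.2.1 carries the qualifier into the analysis: "The proportion of participants hospitalized (COVID-19 related) by Day 28 will be estimated using the Kaplan-Meier method". The log-rank test is kept and a Cox hazard ratio is added.

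Two SAP sections record departures from the protocol that bear on efficacy. SAP 2.3 covers only the cancelled interim review and the enrollment stop behind it: "The DMC analysis was not performed due to the stop of enrollment on 08 April 2021". SAP 6.4 covers only the oxygen endpoint: "The protocol states that the proportion of participants progressing to requiring oxygen supplementation by Day 28 will be estimated using the Kaplan-Meier method", which the SAP replaces with a Fisher exact test.

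**The concern.** This is a change of event definition, not of test, and it has no stated reason. Under the protocol wording, this is the one visible hospitalization efficacy endpoint that does not depend on anyone's judgment of cause. The primary endpoint does depend on it: "The endpoint will be derived by combining the available all-cause death and COVID-19 related hospitalization reported by the site". With the qualifier added, the secondary endpoint becomes the primary composite without its death component. It no longer shows whether the result survives when attribution is ignored.

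Timing adds to the case for disclosure. This SAP was written after enrollment stopped, and SAP 6.4 already refers to how few participants progressed to needing oxygen. Nothing suggests that anyone was unblinded, but a definition changed at that stage should be on record.

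**Working it through.** The point rests on comparing texts. The arithmetic in step 4 only illustrates possible size.

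**1. Is the protocol endpoint unrestricted?** All four statements of it (synopsis, 3.1, 8.1.3, 8.5.2) lack a cause qualifier. In the same lists, each hospitalization or medical-visit composite carries the COVID-19 restriction. Section 8.5.2 applies the restriction to three composites and then omits it for this endpoint. Selective use of the qualifier makes any-cause the natural reading, although the protocol does not write it out.

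**2. Do the two wordings count different people?** Yes. SAP 6.1.3 describes this case: "If a participant has a non COVID-19 related hospitalization first and then dies without experiencing a COVID-19 related hospitalization". There the event is the death, so the unrelated admission is not itself an event. Such an admission counts under the protocol wording and does not count under SAP 6.2.

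**3. Is the change declared?** SAP 2.3 and 6.4 are readable and do not mention it. The revision table in SAP Section 11 is empty. SAP Section 1 promises documentation in the study report only for changes made after the SAP is final, so it does not cover a change already in the SAP.

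**4. How much could it matter?** Inputs from the documents: 584 randomized (SAP 2.1.1), 1:1 allocation, and design composite rates of 12% placebo and 6.6% RDV (Protocol 8.9, SAP 1.3). Assumed, not in the documents: 1% to 2% of each arm has an admission judged unrelated, equally in both arms and with no overlap with composite events.

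- Per arm: 584 / 2 = 292.
- Composite events, deaths included: 0.12 × 292 = 35.0 placebo; 0.066 × 292 = 19.3 RDV.
- Unrelated admissions per arm: 0.01 × 292 = 2.9; 0.02 × 292 = 5.8.
- As a share of placebo events: 2.92 / 35.04 = 8.3%; 5.84 / 35.04 = 16.7%.
- As a share of RDV events: 2.92 / 19.27 = 15.2%; 5.84 / 19.27 = 30.3%.

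Hazard ratio = ln(1 − p_RDV) / ln(1 − p_placebo). With no unrelated admissions this reproduces the plan's own 0.534.

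| Assumed unrelated rate | Risk ratio | Hazard ratio |
|---|---|---|
| 0% | 0.066 / 0.12 = 0.550 | 0.534 |
| 1% | 0.076 / 0.13 = 0.585 | 0.568 |
| 2% | 0.086 / 0.14 = 0.614 | 0.596 |

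**5. Against sampling error.** Expected composite events are 35.0 + 19.3 = 54.3, so the standard error of the log hazard ratio is about 2 / √54.3 = 0.27. The shifts are ln(0.568 / 0.534) = 0.06 and ln(0.596 / 0.534) = 0.11, or about 0.2 and 0.4 standard errors.

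**The case against.** The strongest reply is that the SAP clarifies the endpoint and does not restrict it. Where the protocol means any cause it says so, as with mortality one line above, and this line carries neither label. Sections 8.9 and 8.9.1 and the synopsis use bare hospitalization as shorthand for the COVID-19 related event. Every visible efficacy objective about admissions or visits is limited to COVID-19 related ones. This stands as a reason for caution about intent. But the shorthand occurs inside the phrase for the composite, usually with the full wording nearby, and not for this standalone endpoint. A clarification that changes who counts as an event would still need recording.

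Second, text between SAP 6.2.1 and 6.4 is redacted and might hold an any-cause analysis. That stands, so the point is confined to the visible SAP. It does not cure the silence of 2.3 and 6.4.

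Third, the numerical illustration uses an assumed rate, composite events in place of hospitalizations, all randomized participants in place of the dosed Full Analysis Set, and design rates although SAP 2.3 cites falling hospitalization rates. All of this is true, and the resulting shift is well within sampling error.

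Fourth, the consequence is limited. SAP 3.5 makes the endpoint exploratory. Site staff are blinded (Protocol 5.1.2), so misattribution should not differ by arm. Inpatient admissions are serious adverse events (Protocol 7.1.2) and are tabulated by arm (SAP 7.1.7). Those tables are only a partial substitute: they are organised by body system and preferred term, mix hospitalization with other seriousness criteria, run to 30 days after the last dose, and carry no Kaplan-Meier or log-rank comparison.

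**Conclusion.** The concern holds. The SAP adds a cause restriction that the protocol's endpoint lacks, in both definition and analysis, and the visible change sections do not list it. The mismatch and the omission are matters of text and depend on no assumption. That the protocol meant any-cause hospitalization is the better reading, held with moderate confidence. The numerical effect cannot be determined from the documents; the shift to a risk ratio of 0.58 to 0.61 depends wholly on the assumed 1% to 2% of unrelated admissions. The primary analysis and its type I error are untouched. This should be corrected, but it does not threaten the trial's main conclusion.

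**What to change.** Analyse hospitalization by Day 28 regardless of attributed cause, using the 24-hour acute-care definition, with the protocol's Kaplan-Meier estimate and log-rank test and the Cox hazard ratio that the SAP adds. Keep the COVID-19 related version as an additional analysis, and list and justify it in SAP 6.4. If the sponsor regards the qualifier as a clarification of what the protocol meant, SAP 6.4 should say so and give the reason.

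The cost is one entry in SAP 6.4 and one extra table. No new data are needed: hospitalizations and the cause of each visit are already collected through Day 28 (Protocol 6.3 to 6.5 and Appendix 2, footnote r).
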